## Abstract

### **Objective:**

Low back pain (LBP) is second only to hearing problems as a reason for Veteran disability, and it is the most common cause of disability globally. Although general activity is encouraged in the treatment of LBP, there is no empirical information available on the **specific** types of activities that are beneficial or harmful for patients seen in primary care for LBP. This study will identify those physical activities with short-term (transient) effects on LBP exacerbations (or “flares” of LBP), as well as identifying the long-term (cumulative) effects of such activities on functional recovery.

### **Research Design and Methodology:**

The proposed research will use a novel approach to distinguish the short-term effects on LBP of physical activities from the long-term effects of such activities, by conducting a longitudinal case-crossover study nested within a cohort study. This design accounts for measured and unmeasured confounds by using each case as his/her own control- an entirely observational study that is analogous to a crossover experiment- capitalizing on modern mobile health and actigraphy technology. The primary exposures of interest are 10 self-reported physical activities commonly performed during work and activities of daily living, and actigraphy-assessed physical activity. The primary outcomes are participant-reported “flares” of low back pain (Aim 1) and participant-reported back-related functional limitations (mobility and activities of daily living [ADLs]) at 1-year follow-up, as measured by the Roland-Morris Disability Questionnaire. This observational study will include up to 730 Veterans with LBP aged 18 and older recruited from the VA Puget Sound Health Care System (VAPSHCS). The study will not affect Veterans’ medical care in any way. After verbal informed consent, recruitment, and baseline data collection, study participants will complete frequent, serial electronic “e-Questionnaires” using their own personal electronic devices (personal computer [PC], tablet, or smartphone) over the 1-year period of follow-up. Participants may also wear ActiGraph units for the 1st 4 weeks of follow-up. Long-term outcomes will be assessed by extended e-Questionnaires completed at 1-year follow-up. Aim 1 analyses will examine the short-term effects of 10 specific activity categories on participant-reported flares across all study assessments over 1-year follow-up. Aim 2 analyses will examine associations between the frequency of exposure to 10 specific activity categories over weeks 1-4 of follow-up, and long-term functional recovery at 12 months as defined by the RMDQ. All analyses will use a biopsychosocial framework accounting for potential confounders (sociodemographics, psychological factors, etc.) and effect modifiers, and will include sensitivity analyses to examine the robustness of findings and important study assumptions.

### **Relevance to VA Mission:**

This work will provide completely new, foundational information that will support Veterans with LBP in navigating the complex process of recovery. It will also help VA clinicians to make recommendations regarding return to work and activities for those with LBP. These findings will also inform the development of future activity-based educational treatments for optimizing functional recovery for Veterans with LBP.

## List of Abbreviations

AE	Adverse Event
CDW	Corporate Data Warehouse
CPRS	Computerized Patient Record System
CSQ	Coping Strategies Questionnaire
DMAP	Data Management and Access Plan
EHR	Electronic Health Record
EMR	Electronic Medical Record
ERIC	Epidemiologic Research and Information Center
FLAReS	Flares of Low Back Pain with Activity Research Study
HIPAA	Health Insurance Portability and Accountability Act
HR	Human Resources
HSR&D	Health Services Research & Development
ICD	International Classification of Diseases
IRB	Institutional Review Board
IRQ	Initial Review
JIT	Questionnaire Just-In-Time
LBP	Low Back Pain
LSRS	Lumbosacral Radicular Syndrome
NIH	National Institutes of Health
NRS	Numerical Rating Scale
OASC	Organizational Assessment Sub-Committee
OR	Odds Ratio
PACT	Patient-Aligned Care Team
PC	Personal Computer
PCL-C	Post-traumatic Stress disorder Checklist
PCP	Primary Care Provider
PHI	Protected Health Information
PHQ-8	8-Item Patient Health Questionnaire
PI	Principal Investigator
PRAF	Project Revision/Amendment Form
PROMIS	Patient-Reported Outcomes Measurement Information System
PTSD	Post-Traumatic Stress Disorder
RMDQ	Roland-Morris Disability Questionnaire
RR&D	Rehabilitation Research & Development
RTW	Return to Work
SAE	Serious Adverse Event
SISQ	Single Item Stress Questionnaire
SLSS	Symptomatic Lumbar Spinal Stenosis
TSK	Tampa Scale of Kinesiophobia
UAP	Unanticipated Problem
UW	University of Washington
VA	Veterans Affairs
VAPS	VA Puget Sound
VAPSHCS	VA Puget Sound Health Care System
VISTA	Veterans Information Systems and Technology Architecture

## 2.0 Introduction

Low back pain (LBP) is the #1 cause of disability worldwide and a leading cause among Veterans. The general advice to remain active when experiencing acute or chronic LBP is a key part of clinical practice guidelines. However, existing guidelines provide no specific recommendations about the types of activity (e.g., lifting, bending, etc.) that should be engaged in or avoided ("Which?") or the duration/intensity of such activities should they be performed ("How?"). The guidelines therefore do not address a major concern of patients with LBP, which is that certain activities may have short-term effects on pain exacerbations or "flares", or cause sustained detrimental effects on pain or function. The distinctions between healthy, benign, and detrimental activities are also important to clinicians, who are often called upon to complete "work restriction forms" as part of the process of making return-to-work (RTW) decisions. An ideal set of work restrictions for persons with LBP would limit only those activities that are likely to cause flares of pain (**transient** effects) or poor overall functional recovery in the longer term (**cumulative** effects). However, there exist no empirically derived data concerning the transient vs. cumulative effects of specific activities during LBP, with which to guide work restrictions.

A typical "work restriction form" excerpt from California state is shown in **Figure 1**, listing 10 categories of activities relevant to LBP. These activities can occur commonly in the workplace, or in other aspects of everyday life. In the absence of empirical data, primary care providers' work restrictions mirror their general practice style or personal beliefs, which may conflict with evidence-based care, and may limit functional recovery if overly restrictive. Primary care providers (PCPs) may feel compelled to choose restrictions that avoid conflict with patients. These factors combine to create a situation where most PCPs feel ill-prepared or conflicted when making work restrictions.

**Our proposed work will yield objective data regarding the risks associated with specific types of activities during LBP, meeting an important need of both Veteran patients and PCPs.**

The expected age range of study participants is 18 years of age and older. We expect the general health status of the subject population to be about average for Veterans' ages. We will not include patients from special classes of subjects or vulnerable populations such as pregnant women, children, cognitively impaired persons, or prisoners due to possible coercion. We will not otherwise make any exclusions based on gender, sex, race, ethnicity, or any minority group designation. VA employees may be enrolled in the study; however, if enrolled, they cannot complete assessments on their VA paid time. "Questionnaires" or "e-Questionnaires" as

**Figure 1. CA State work restriction form**

The Employee can work with the following restrictions:

	hours: 1-2	2-4	4-6	6-8	None
Standing					
Walking					
Sitting					
Climbing					
Forward Bending					
Kneeling					
Crawling					
Twisting					

Lift/Carry Restrictions: May not lift/carry at a height of \_\_\_\_\_  
more than \_\_\_\_\_ lbs. for more than \_\_\_\_\_ hours per day.

referred to in this Protocol do not fall under the definition of “surveys” as used in the VA Survey Guidance document. As such, OASC and local VAPS HR will not be notified if a VA employee enrolls in this study. The term “e-Questionnaires” is used in materials related to human subjects approvals, but the term “e-Surveys” is used in participant-facing materials, due to the simplicity and brevity of the term “e-Survey”.

### 3.0 Objectives

#### **Aim 1: Estimate the short-term effects (<24 hours) of specific physical activities on pain flares in Veterans with LBP.**

*Research question #1: What are the short-term (transient) effects (<24 hours) of specific types of physical activities on pain flares in Veterans with LBP?*

We will conduct a longitudinal case-crossover study with 1-year follow-up to identify activities that trigger flares among up to 730 Veterans of working age (18-65 yrs) seen in VA primary care for LBP. The predictors of interest are 10 activity categories relevant to LBP that are commonly included in work restriction forms used for RTW determinations. The primary outcome is a validated flare definition characterized by pain and functional impact. Analyses will use a biopsychosocial framework accounting for key potential confounders and moderators, such as pain characteristics, work-related factors, catastrophizing, fear of movement, depression, stress, post-traumatic stress, and analgesic use.

#### **Aim 2: Estimate the long-term effects of specific physical activities among Veterans with LBP.**

*Research question # 2: What are the long-term (cumulative) effects of specific types of physical activities on functional recovery at 1-year follow-up?*

In analyses of the longitudinal cohort within which the Aim 1 case-crossover study is nested, we will examine associations between the frequency of activities for 10 specific activity categories over the first 4 weeks of follow-up, and long-term LBP-related functional recovery as defined by the Roland-Morris Disability Questionnaire (RMDQ) at 1-year follow-up (primary outcome). Analyses will account for a range of important potential confounders and moderators, using a biopsychosocial framework, as in Aim 1. Secondary outcomes will include average pain intensity, lost work productivity, and quality of life, and analgesic use at 12 months.

These study aims will produce tables of evidence-based estimates contrasting the short-term risks of specific physical activities on LBP flares with the long-term effects on functional recovery. These data will then be used to design educational interventions to optimize physical activity, considering both the short- and long-term effects of physical activities.

#### Recruitment in additional populations (project modification, January 2023)

In December 2022, we obtained sponsor approval from ORD RR&D to expand the target population of recruitment (beyond Veterans who have recently been seen in for back pain in VAPSHCS primary care, the “*original target population*”), in order to achieve the original recruitment goal of 440 Veterans who complete 1-year follow-up. In the current project modification, we expand recruitment to other Veterans with low back pain who have been seen in VAPSHCS (the “*expanded target population*”), but may not have had recent visits for back pain in VAPSHCS primary care. We will not contact individuals who have already been contacted once as part of recruitment efforts using the Information Statement (targeted to the original target population). The approach and analyses for the main study aims as stated above will not change; these main study aims will involve only the study sample recruited from the *original target population* (Veterans seen for low back pain in primary care). However, we will also conduct separate, analogous analyses, among Veterans recruited from the *expanded target population*. For certain analyses where exposure-outcome relationships do not differ between samples recruited from the original target population vs. the expanded target population, we will conduct secondary analyses pooling the two samples.

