## 5.1 Study Design

This will be an ***observational***, longitudinal case-crossover study nested within a cohort study, following up to 730 Veterans seen for LBP in VA primary care prospectively for 12 months. Study procedures will not make changes to nor in any way affect the typical medical care for LBP provided at VAPSHCS. **All study assessments following recruitment will be “e-Questionnaires” that participants complete using their own personal electronic devices (smartphones, tablets, or PCs, not provided by the study).** There are two types of e-Questionnaires that participants will complete: “*scheduled e-Questionnaires*” and “*flare window e-Questionnaires*”. Scheduled e-Questionnaires are quasi-random, ‘cue-elicited’ frequent assessments that will be repeated numerous times throughout the 1-year follow-up period. Cues to complete scheduled e-Questionnaires are automated “e-Alert” notifications sent by text message and email at the start of each “*scheduled assessment window*”, the 3-hour period during which a scheduled e-Questionnaire may be completed. ***Scheduled e-Questionnaires will occur three times each week during weeks 1-4 of follow-up, once a week during weeks 5-8, and twice a month during months 2-12.*** Participants will also complete unscheduled “*flare window e-Questionnaires*” on an *ad hoc* basis, if they experience new flares of LBP at any time during the 1-year follow-up period. At study entry, participants will receive training on how to complete flare window e-Questionnaires, if they experience flares of pain, by logging on to a secure Participant Portal (the **Flares of LBP with Activity Research Study** or “FLARES” website) within 3 hours after the onset of a new pain flare. In addition, all scheduled e-Questionnaires will remind participants to complete a flare window e-Questionnaire if they have a new pain flare. Scheduled e-Questionnaires and flare window e-Questionnaires generally contain the same question items, however, scheduled e-Questionnaires inquire about activity exposures *preceding the start of the scheduled assessment window* (when e-Alert notifications are sent), and flare window e-Questionnaires inquire about activity exposures *over the time period preceding the flare onset*. Each e-Questionnaire will begin by prompting the participant with the definition of a LBP flare. Participants will then report whether or not they are experiencing a flare, the primary outcome for Aim 1 of this study. E-Questionnaires will also inquire about activity exposures that have occurred over the 24-hour period prior to the assessment window start and - *if* an activity is reported – ask for further clarification of whether the activity was performed in the 2-hour period prior to the assessment window start. Further questions included in every e-Questionnaire are time-varying pain and psychological covariates (pain intensity, depression, catastrophizing, stress, etc.) assessed using brief, validated measures. All e-Questionnaires are inherently time lagged for activity-flare relationships, since they capture *current* flare status at time=t, and activities in the 24-hour period *before* the start of the assessment window/flare onset (t-1). Participants may also be offered to wear the optional ActiGraph wGT3X-BT unit continuously for weeks 1-4 of the study. Due to the participant burden involved with frequent serial e-Questionnaire assessments, a run-in period during weeks 1 and 2 of follow-up will exclude those individuals unable to maintain compliance with these assessments. Aim 1 analyses will examine the short-term effects of 10 specific activity categories on participant-reported flares across all study assessments over 1-year follow-up. Aim 2 analyses will examine associations between the frequency of exposure to 10 specific activity categories over weeks 1-4 of follow-up, and long-term functional recovery at 12 months as defined by the RMDQ. All analyses will use a biopsychosocial framework accounting for potential confounders (sociodemographics, psychological factors, etc.) and effect modifiers, and will include sensitivity analyses to examine the robustness of findings and important study assumptions.

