### **Description of Study Population/Expected Enrollment/Vulnerable Populations:**

We expect to recruit up to 730 Veterans in the proposed study in order to obtain at least 440 Veterans who complete 1-year follow-up. Further details of inclusion/exclusion criteria are provided below in Table 1 (see Section 5.4). All participants recruited will be Veterans. We will recruit Veterans from primary care clinics and other clinic encounters (including telephone visits) occurring at VAPSHCS. The anticipated age range of participants is between 18 years and 65 years of age. In expanded recruitment as part of a project modification (January 2023), recruitment was also expanded to other Veterans with low back pain who have been seen at VAPSHCS or through VA-associated community care, but not necessarily in VAPSHCS primary care specifically. Patients with severe and major active medical and psychiatric comorbidities will be excluded since they will likely be unable to complete the study procedures, particularly the requirements for frequent serial assessments in the first 4 weeks of follow-up. Otherwise, we expect the general health status of the subject population to be about average, for Veterans' ages. We will exclude Veterans from special classes of subjects or vulnerable populations such as pregnant women, children, cognitively impaired persons, or prisoners, to avoid possible coercion of vulnerable populations. We will not otherwise make any exclusions based on gender, sex, race, ethnicity, or any minority group designation. The study inclusion and exclusion criteria are specifically defined to capture the broadly-defined target population of Veterans seen for LBP seen in primary care, who are of working age (18-65 years), irrespective of whether participants are actually currently employed. We will re-contact any participants who were interested in the study and screened, but failed criteria from a prior version of the Screening Checklist, provided that they meet all criteria on the currently approved version of the Checklist.

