## **5.2 Recruitment Methods**

We will recruit up to 730 participants from among Veterans seeking care at VAPSHCS. The eligibility and exclusion criteria are defined to capture the medically eligible target population of Veterans seeking care for LBP.

Where not stated [or indicated otherwise in blue font \(signifying UW \[non-VA\] research processes\)](#), all aspects of the descriptions below pertain to the [VA component](#) of the proposed research.

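### Power for both aims is stated at 440 Veterans, but recruits added to reach 440 are excluded from the main aims, and no original-population number is given

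*Combined protocol and SAP*

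**What the plan says.** **The modification (Section 3.0, Recruitment in additional populations).** Recruitment is widened "in order to achieve the original recruitment goal of 440 Veterans who complete 1-year follow-up". On the analyses, "The approach and analyses for the main study aims as stated above will not change", and "these main study aims will involve only the study sample recruited from the" original target population. The expanded sample gets separate, analogous analyses. Pooling the two samples is secondary, and limited to certain analyses where the exposure-outcome relationships do not differ.

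**The sample size (Section 5.6.1).** Of 730 recruited, 290 (40%) are expected to have limited data, leaving 440. At alpha 0.005 and n=440, the text gives:

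- Aim 1: about 90% power for OR 1.5 at an activity frequency of about 10%; 80% for OR 1.6 at 5%; 80% for OR 1.81 at 3%.
- Aim 2: at least 80% power for a 2.5-point RMDQ difference, where that difference corresponds to a 65% change in activity frequency.

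It closes with a planned 730 for each aim and does not mention the expansion.

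**What 730 refers to.**

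- Section 3.0, Aim 1: "among up to 730 Veterans of working age (18-65 yrs) seen in VA primary care for LBP".
- Section 5.1: "following up to 730 Veterans seen for LBP in VA primary care prospectively for 12 months".
- Section 5.1, study population paragraph: "We expect to recruit up to 730 Veterans in the proposed study in order to obtain at least 440 Veterans who complete 1-year follow-up". The same paragraph adds that "recruitment was also expanded to other Veterans with low back pain who have been seen at VAPSHCS or through VA-associated community care".
- Section 5.2: "We will recruit up to 730 participants from among Veterans seeking care at VAPSHCS".

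**The concern.** The modification gives the added recruits a purpose, reaching 440 completers, and then keeps them out of the analyses for which 440 was calculated. If the original population were on course to supply 440 on its own, the stated reason for expanding would not arise. The natural reading is therefore that the main aims will rest on fewer than 440, while the only power statement in the text is for 440.

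The ceiling of 730 does not settle this. Two places attach it to primary-care patients and two to the study's recruitment as a whole, so it is not a count of either population.

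What is at stake is interpretation. The study will produce a table of activities with and without detectable effects, intended to inform activity advice. A reader who believes the main analyses had the stated power will give a null result more weight than it may deserve, especially for the less common activities, where the stated power is 80% with no margin. Bias and type I error are not in question.

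**Working it through.** **1. The plan's own figures.** 0.05/10 = 0.005. 730 − 290 = 440, and 290/730 = 39.7%. Inflating 440 for 40% loss gives 440/0.60 = 733.3, or 734, against the stated 730. These agree. The simulated powers cannot be rebuilt from the text, which omits the flare rate and the exposure variance. A separate conditional-logistic simulation for Aim 1 (400 replications; assumed 36 windows per person, 7.5% flare prevalence, between-person SD of 1 on the logit scale) gave 94%, 80% and 81% at n=440, compatible with the stated 90%, 80% and 80%.

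**2. Power at a smaller n.** The documents give no original-population number, so each n below 440 is an assumption. Alpha is taken as two-sided; Section 5.6.1 does not state sidedness. Holding the plan's information per person fixed:

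Power(n) = Φ[(2.807 + z_stated) × √(n/440) − 2.807],

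where 2.807 = z(0.9975), z(0.90) = 1.282 and z(0.80) = 0.842. For example, at n=350 from 90%: 4.089 × 0.892 − 2.807 = 0.84, and Φ(0.84) ≈ 0.80.

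| Assumed n | Stated 90% becomes | Stated 80% becomes |
|---|---|---|
| 400 | 86% | 75% |
| 380 | 84% | 72% |
| 350 | 80% | 67% |
| 320 | 75% | 62% |

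The same simulation run at n=350 gave 80%, 65% and 68% for the three Aim 1 scenarios, in line with the table.

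**3. Break-even points.** n = 440 × [(2.807 + z_target)/(2.807 + z_stated)]².

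- The 90% case reaches 80% at 440 × (3.649/4.089)² ≈ 350, a shortfall of 90.
- The 80% cases reach 70% at 440 × (3.331/3.649)² ≈ 367. Within the plan's calculation, any shortfall takes them below 80%.

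**4. Detectable odds ratios at 80% power (Aim 1).** exp[ln(OR) × √(440/n)].

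| OR at n=440 | n=380 | n=350 | n=320 |
|---|---|---|---|
| 1.60 (frequency 5%) | 1.66 | 1.69 | 1.74 |
| 1.81 (frequency 3%) | 1.89 | 1.94 | 2.0 |

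**5. Detectable RMDQ difference at 80% power (Aim 2).** 2.5 × (3.649/(2.807 + z_true)) × √(440/n). The plan says only that power at 440 is at least 80%, so two values of the true power are shown. The first is the upper bound.

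| True power at 440 | n=380 | n=350 | n=320 |
|---|---|---|---|
| 80% | 2.69 | 2.80 | 2.93 |
| 90% | 2.40 | 2.50 | 2.62 |

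**The case against.** The shortfall is inferred. The modification does not say how far short the original population is or that its recruitment has stopped, and Section 5.2.3 still describes recurring identification of primary-care patients. This stands: the figures above illustrate and do not estimate.

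The 440 in the modification counts one-year completers, and Aim 1 uses every scheduled and flare-window questionnaire, so completion is not required. Section 5.6.1 also calls its Aim 1 estimate conservative, because it ignores flare-window data and all data from the 290. This stands in part. True Aim 1 power may exceed the stated figure and could absorb a modest shortfall, but the plan does not quantify the margin.

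Section 5.6.1 expects activity frequencies of 5–25%, so the two 80% cases lie at or below the bottom of that range, and the detectable odds ratios stay within the 1.5–2.0 that the plan regards as meaningful down to about n=320. That is correct and limits the consequence for Aim 1.

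For Aim 2, adjusting for baseline RMDQ could recover precision. With an assumed baseline-to-1-year correlation of 0.5, little exposure-covariate correlation and a simulation that left the adjustment out, residual variance falls by 25%, and 330 adjusted would match 440 unadjusted (440 × 0.75). The documents confirm none of these conditions. The telephone Exit Survey (Section 5.5) and multiple imputation (Section 5.6.2) may also recover outcomes, but for the main aims only among people enrolled from the original population.

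Figure 2 is not shown in the text available and may plot other sample sizes for Aim 1. The Aim 2 text cites no figure and varies only the strength of the association, at n=440.

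**Conclusion.** The concern holds. The modification confines the main aims to a population that, on its own stated reason for expanding, was not expected to reach 440 completers. The text of Section 5.6.1 still attaches n=440 to both aims, and no section gives a number for that population. If 730 and 440 are in fact meant for the original population alone, Section 5.6.1 fits, but the document does not say so.

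The size depends on the unknown n. A shortfall of 40 costs about 4 to 5 percentage points of power, and a shortfall of 90 about 10 to 13. For Aim 2 at a shortfall of 90, the detectable difference is at most about 2.8 points, and still 2.5 if true power at 440 was 90%. These figures assume a two-sided alpha of 0.005 and unchanged information per person. This should be fixed. Confidence is medium, because the shortfall itself is not documented.

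**What to change.** In Section 5.6.1, give the actual or projected number of original-population participants analysable for Aim 1 and, separately, for Aim 2. Restate power or the detectable effect for each aim at those numbers. Say whether 730 and 440 are study totals or original-population numbers, and bring Aim 1 in Section 3.0, the opening and study population paragraphs of Section 5.1, and Section 5.2 into line with that answer. Keep the original-population analysis primary and pooling secondary, as now.

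The cost is a few restated figures and sentences, with no new participants, data or analyses. The one drawback is that the stated power may look less favourable.
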